7.2.4.2 Creatinine clearance

Creatinine clearance will be estimated using Cockcroft-Gault formula (7):

$$CCr = (140 - \text{Age}(\text{years})) \times \text{Weight} (\text{kg}) \times [0.85 \text{ if female}] / 72 \times [\text{Serum Creatinine} (\text{mg/dL})]$$

Chronic Kidney Disease will be categorized according to these values, included in Clinical Practice Guidelines for Chronic Kidney Disease: Evaluation, Classification, and Stratification:

- ≥ 90 : Kidney damage with normal or increased glomerular filtration rate (GFR)
- 60-89: Kidney damage with mild decreased GFR
- 30-59: Moderate decrease in GFR
- 15-29: Severe decrease in GFR
- < 15 : Kidney failure

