7.2.17 Underdosed or overdosed patient (current NOAC treatment)

The recommended dose of dabigatran is 150mg twice a day (BID). Patients who meet any of the following criteria should perform a dose adjustment to 110mg BID, so those who receive the recommended dose of 150mg BID will be classified as overdosed. Those who receive a 110mg BID dose and do not meet any of the following criteria will be classified as underdosed:

- Age ≥ 80 years
- Patients aged 75-79 years and HAS-BLED ≥ 3
- Moderate renal impairment (creatinine clearance 30-50mL/min)

The recommended dose of rivaroxaban is 20mg once a day (QD). Patients who meet the following criteria should perform a dose adjustment to 15mg QD, so those who receive the recommended dose of 20mg QD will be classified as overdosed. Those who receive a 15mg QD dose and do not meet following criteria will be classified as underdosed:

- Moderate renal impairment (creatinine clearance 30-50mL/min) or severe renal impairment (creatinine clearance 15-29mL/min)

The recommended dose of apixaban is 5mg BID. Patients who meet at least 2 of the following 3 criteria should perform a dose adjustment to 2.5mg BID, so those who receive the

Document:	H:\HOR-Europe\2019\2512352 - Study on anticoagulation management - BI\Proyecto\Estadistica\SAP\S		
	AP_REBELD_version1.0_08072020.docx		
Author:		Version Number:	Version 1.0
		Version Date:	[08072020]

Template No.: RWI_TP_BIOS0013 Revision 1

Reference: RWI_WI_BIOS0015

Effective Date: 15Jun2018

recommended dose of 5mg BID will be classified as overdosed. Those who receive a 2.5mg BID dose and do not meet at least 2 of the 3 following criteria will be classified as underdosed:

- Age \geq 80 years
- Body weight \leq 60 kg
- Serum creatinine \geq 1,5 mg/dl or severe renal impairment (creatinine clearance 15-29mL/min)

The recommended dose of edoxaban is 60mg OD. Patients who meet at least 1 of the following 2 criteria should perform a dose adjustment to 30mg OD, so those who receive the recommended dose of 60mg OD will be classified as overdosed. Those who receive a 30mg OD dose and do not meet at least 1 of the 2 following criteria will be classified as underdosed:

- Body weight \leq 60 kg
- Moderate or severe renal impairment (creatinine clearance 15-50mL/min)

A categorical variable for dose category with 3 levels will be described:

- 1) Appropriately dosed
- 2) Underdosed
- 3) Overdosed.

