9. OUTPUT PRESENTATIONS

Tables and Figures on page 42 describe the presentations for this study and therefore the format and content of the summary TLFs to be provided by [REDACTED]

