14.6 Exploratory analysis

History and current antiplatelet treatment will be described by current NOAC type.

Treatment received at the time of thromboembolic and bleeding events will be described, including NOAC, VKA and antiplatelet treatments.

Doses of current NOAC treatment received by the patient will be described according to HAS-BLED score (as low, intermediate and high risk).

The percentage of underdosed and overdosed patients for current NOAC treatment will be described.

HAS-BLED total score (as <3 , $3-5$, ≥ 5) will be described according to NOAC and antiplatelet current treatment.

Multivariate logistic regression will be used to evaluate the association between the Clinical Frailty Scale (dependent variable: Frailty patients - CFS scoring >4 vs Non-frailty patients - CFS scoring ≤ 4) and the thromboembolic and the bleeding events (independent variables). To calculate this analysis, only events that have occurred subsequent to the start of anticoagulant therapy (not those prior to the start of VKA / NOACs) will be considered. Other factors will be age, sex, BMI, smoking habit, alcohol consumption, time since NVAf diagnosis, NVAf type, modified EHRA scale, procedures and interventions, comorbidity Charlson index and clinical risk factors. Univariate analysis will be performed. All variables which have a P value of less than 0.1 will be included in the multivariate analysis.

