NOAC	Valid N* No				

Document: H:\HOR-Europe\2019\2512352 - Study on anticoagulation management - BI\Proyecto\Estadística\SAP\SAP_REBELD_version1.0_08072020.docx

Author: [REDACTED] Version Number: Version 1.0
Version Date: [08072020]

Template No.: RWI_TP_BIOS0013 Revision 1

Reference: RWI_WI_BIOS0015

Effective Date: 15Jun2018

		Nasal	Pulmonary	Articular-muscular	Conjunctival
	Yes N missing				
Type of NOAC	Valid N Dabigatran Rivaroxaban Apixaban Edoxaban N missing				
Antiplatelet	Valid N* No Yes N missing				
Type of antiplatelet	Valid N Aspirin Clopidogrel Prasugrel Ticlopidine Ticagrelor Cilostazol Triflusal Dipyridamole Others N missing				

*Number of events in each column

One event could be associated with more than one treatment

Table 50. Current NOAC dose according to HAS-BLED

		HAS-BLED			
		Low risk	Intermediate risk	High risk	Total
Dabigatran dose	Valid N 110mg BID 150mg BID N missing				
Rivaroxaban dose	Valid N				

Document: H:\HOR-Europe\2019\2512352 - Study on anticoagulation management - BI\Proyecto\Estadística\SAP\SAP_REBELD_version1.0_08072020.docx

Author: [REDACTED] Version Number: Version 1.0
Version Date: [08072020]

Template No.: RWI_TP_BIOS0013 Revision 1

Reference: RWI_WI_BIOS0015

Effective Date: 15Jun2018

		HAS-BLED			
		Low risk	Intermediate risk	High risk	Total
	15mg QD 20mg QD N missing				
Apixaban dose	Valid N 2.5mg BID 5mg BID N missing				
Edoxaban dose	Valid N 30mg QD 60mg QD N missing				

Table 51. Overdosing and underdosing of current NOACs

		Appropriately dosed (n,%)	Underdosed (n,%)	Overdosed (n,%)
Dabigatran	Dabigatran (Age <80 years)			NA
	Dabigatran (Age ≥80 years)		NA	
	Dabigatran (75-79 years and HAS-BLED < 3)			NA
	Dabigatran (75-79 years and HAS-BLED ≥ 3)		NA	
	Dabigatran (creatinine clearance >50mL/min)			NA
	Dabigatran (creatinine clearance 30-50mL/min)			NA
Rivaroxaban	Rivaroxaban (creatinine clearance >50mL/min)			NA

Document: H:\HOR-Europe\2019\2512352 - Study on anticoagulation management - BI\Proyecto\Estadística\SAP\S AP_REBELD_version1.0_08072020.docx

Author: [REDACTED] Version Number: Version 1.0
Version Date: [08072020]

Template No.: RWI_TP_BIOS0013 Revision 1

Reference: RWI_WI_BIOS0015

Effective Date: 15Jun2018

		Appropriately dosed (n,%)	Underdosed (n,%)	Overdosed (n,%)
	Rivaroxaban (creatinine clearance ≤ 50 mL/min)		NA	
Apixaban	Apixaban (Age < 80 years)			NA
	Apixaban (Age ≥ 80 years)		NA	
	Apixaban (Body weight > 60 kg)			NA
	Apixaban (Body weight ≤ 60 kg)		NA	

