	Apixaban (Serum creatinine $< 1,5$ mg/dl or creatinine clearance ≥ 30 mL/min)			NA
	Apixaban (Serum creatinine $\geq 1,5$ mg/dl or creatinine clearance < 30 mL/min)		NA	
Edoxaban	Edoxaban (Body weight > 60 kg)			NA
	Edoxaban (Body weight ≤ 60 kg)		NA	
	Edoxaban (creatinine clearance > 50 mL/min)			NA
	Edoxaban (creatinine clearance 15-50 mL/min)		NA	

Table 52. HAS-BLED score according NOAC+antiplatelet current treatment

		HAS-BLED score				
		Valid N	< 3	3-5	≥ 5	N missing
Current treatment	Dabigatran+aspirin					
	Dabigatran+clopidogrel					
	Dabigatran+peasugrel					
	...					
	... (for all combinations)					

Row percentage will be calculated

Document: H:\HOR-Europe\2019\2512352 - Study on anticoagulation management - BI\Proyecto\Estadistica\SAP\S AP_REBELD_version1.0_08072020.docx

Author: [REDACTED]

Version Number:

Version 1.0

Version Date:

[08072020]

Template No.: RWI_TP_BIOS0013 Revision 1

Reference: RWI_WI_BIOS0015

Effective Date: 15Jun2018

Table 53. Multivariate logistic model to evaluate the association between the Clinical Frailty Scale and the thromboembolic and the bleeding events

Variable	Estimate	Standard error	t-value	Pr> t	OR

*dependent variable: CFS in two categories: Frailty patients - CFS scoring >4 vs Non-frailty patients - CFS scoring ≤4)

*independent variables: thromboembolic and bleeding events. Other factors will be age, sex, BMI, smoking habit, alcohol consumption, time since NVAF diagnosis, NVAF type, modified EHRA scale, procedures and interventions, comorbidity Charlson index and clinical risk factors. Univariate analysis will be performed and all variables which have a P value of less than 0.1 will be included in the multivariate analysis.

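### SAP Table 51: the first apixaban renal row uses *or* where the complement of the second row needs *and*, so patients discordant on creatinine and clearance fit both rows

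*SAP*

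**What the plan says.** SAP 7.2.17 defines under- and overdosing. For apixaban, "Patients who meet at least 2 of the following 3 criteria should perform a dose adjustment to 2.5mg BID"; patients on 2.5 mg BID who "do not meet at least 2 of the 3 following criteria will be classified as underdosed". The three criteria are age 80 or over, weight 60 kg or less, and a renal criterion that reads, after the creatinine limit of 1.5, "mg/dl or severe renal impairment (creatinine clearance 15-29mL/min". The renal criterion is thus met when either part is met.

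SAP 14.6 plans the description: "The percentage of underdosed and overdosed patients for current NOAC treatment will be described". Table 51 in section 17.4 is its shell. It gives apixaban three pairs of rows, for age, weight ("Apixaban (Body weight" above or up to 60 kg) and renal function, against the columns appropriately dosed, underdosed and overdosed. In the renal pair both rows contain "mg/dl or creatinine clearance":

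- first row: creatinine <1.5 *or* clearance ≥30, with Overdosed set to NA;
- second row: creatinine ≥1.5 *or* clearance <30, with Underdosed set to NA.

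The age and weight pairs have the same NA pattern. SAP 9 says that the tables and figures "describe the presentations for this study and therefore the format and content of the summary TLFs".

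**The concern.** The age rows and the weight rows are true complements, so each patient has one label per pair. The renal pair is not: negating an *or* condition gives an *and* condition, and the first row keeps the *or*. Nothing in the table or text says where a patient goes who meets only one part of the renal criterion.

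Section 9 makes the shells the specification for format and content. A program written literally from this one could count discordant patients twice, or place patients who meet the renal criterion in the row for those who do not. Table 51 is the only shell in the public SAP for the dosing description, and dosing errors in the elderly are part of the study's rationale (protocol section 7).

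**Working it through.** **Inputs.** Row labels and NA cells from SAP Table 51; the renal criterion and the 2-of-3 rule from SAP 7.2.17; clearance from SAP 7.2.4.2 ("Creatinine clearance will be estimated using Cockcroft-Gault formula"); age 75 or over from the inclusion criteria. The plan states no figure to reproduce here.

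**Step 1, logic.** NOT (creatinine ≥1.5 OR clearance <30) = (creatinine <1.5 AND clearance ≥30). Applying the printed labels:

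| Creatinine, mg/dl | Clearance, mL/min | First row | Second row |
|---|---|---|---|
| 1.0 | 60 | yes | no |
| 1.8 | 25 | no | yes |
| 1.7 | 45 | yes | yes |
| 1.0 | 25 | yes | yes |

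Only the two discordant patterns fit both rows.

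**Step 2, can discordance occur at this age?** Clearance = (140 − age) × weight × (0.85 if female) / (72 × creatinine).

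- Man, 80 years, 75 kg, creatinine 1.6: 4500/115.2 = 39.1. Both labels.
- Man, 78 years, 80 kg, creatinine 1.6: 4960/115.2 = 43.1. Both labels.
- Woman, 85 years, 60 kg, creatinine 1.4: 2805/100.8 = 27.8. Both labels.

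On a grid of ages 75 to 95, weights 45 to 100 kg, creatinine 0.6 to 2.5 and both sexes, restricted to clearance of at least 15, 2121 of 9711 profiles satisfy both labels (1695 with creatinine ≥1.5 and clearance ≥30; 426 with creatinine <1.5 and clearance <30). None satisfies neither. With *and* in the first row, none satisfies both and none satisfies neither.

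**Step 3, do discordant patients meet the 7.2.17 criterion?** Yes, except where creatinine is <1.5 and clearance is below 15. A woman of 95 years, 40 kg, creatinine 1.49 has clearance 1530/107.28 = 14.3. She is in the <30 row but outside 15-29. She meets age and weight anyway, so her dose category does not depend on the renal part.

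**Step 4, consequence if the rows report the patient-level category.** Take age ≥80, weight ≤60 kg, creatinine ≥1.5, clearance <30 (each yes or no) and dose (2.5 or 5 mg): 2^5 = 32 combinations, classified by the 2-of-3 rule. Half (16) are discordant, and all of these meet the renal criterion.

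- Discordant and appropriately dosed: 8, counted in both rows.
- Discordant and underdosed (2.5 mg, no other criterion): 2, counted only in the first row, because Underdosed is NA in the second. Wrong row.
- Discordant and overdosed: 6, counted only in the second row. Correct.
- Both renal parts met: 8, of which 7 are correct and 1 has no cell (2.5 mg, no other criterion).
- Neither part met: 8, of which 7 are correct and 1 has no cell (5 mg, age and weight both met).

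Total: 6 + 7 + 7 = 20 correct, 8 twice, 2 in the wrong row, 2 in no cell. With *and* alone: 28 correct, 4 in no cell. Opening Underdosed in the second row gives 31, and opening Overdosed in the first gives 32.

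The first man above, on 2.5 mg, meets age and renal, is appropriately dosed and is counted twice. The second man meets renal only: on 2.5 mg he is underdosed and appears only in the first row; on 5 mg he is appropriately dosed and counted twice. The woman, on 5 mg, is overdosed and correctly appears only in the second row.

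**Step 5, age and weight pairs.** Under the same reading, 2 of 16 combinations (age, weight, renal, dose) have no cell in each pair. A man of 82, 70 kg, creatinine 1.0 (clearance 4060/72 = 56.4) on 2.5 mg meets age only and is underdosed, but Underdosed is NA in the age ≥80 row. A woman of 77, 55 kg, creatinine 1.5 (2945.25/108 = 27.3) on 5 mg meets weight and renal and is overdosed, but Overdosed is NA in the age <80 row.

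**The case against.** The derivation that governs is sound. SAP 11.1 refers derived variables to section 7.2, and 7.2.17 has the renal *or* right, inside the 2-of-3 rule. A careful programmer would probably read the first row as the complement of the second. This stands, and it is why the point is a label slip in a mock table and no more. It does not remove the slip, because no text tells the programmer to read the row that way.

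The tally in step 4 depends on a reading that the SAP does not state: that each row cross-tabulates the patient-level category and that NA cells drop patients. The NA pattern also fits a display that judges dose on one criterion at a time, although that contradicts the 2-of-3 rule. Under that reading all 16 discordant combinations fall in both rows with different categories: on 2.5 mg, underdosed in one and appropriately dosed in the other. This objection stands too. The overlap of labels is certain; the 20/8/2/2 split is conditional.

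A reader might also infer that 7.2.17 should be rewritten from 15-29 to below 30 to match the table. The documents do not support that. Section 7.2.17 uses a floor of 15 for rivaroxaban, apixaban and edoxaban alike. The edit could change a dose category only with creatinine <1.5, clearance <15 and exactly one of the age and weight criteria met. For a woman over 60 kg that needs 140 − age < 15 × 108/(60 × 0.85) = 31.8, so an age above 108; for a woman of 79 it needs a weight below 15 × 108/(61 × 0.85) = 31.2 kg.

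Finally, the NA conflict is not confined to apixaban. Under 7.2.17 a dabigatran patient aged 75-79 with HAS-BLED ≥3 on 150 mg is overdosed, but Overdosed is NA in the age <80 row. All patients on 150 mg with clearance 30-50 are overdosed, yet that row also shows NA there. An edoxaban patient above 60 kg with clearance 40 on 60 mg is overdosed, but Overdosed is NA in the weight >60 kg row.

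**Conclusion.** The first apixaban renal row is wrong as printed, and this follows from the labels alone. Patients discordant on creatinine and clearance satisfy both rows, although nearly all of them meet the renal criterion.

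The size is minor. The effect is limited to one exploratory descriptive table. The patient-level dose category of 7.2.17, and the primary and secondary outcomes, are unaffected. A reader might take 8 of 32 combinations, or 2121 of 9711 grid profiles, as the share of patients miscounted. Neither is: both count possibilities, and the documents give no joint distribution of creatinine and clearance from which a share could be derived. Nor do the documents support the inference that the study's under- and overdosing percentages are wrong; programmed from 7.2.17, they are not.

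The NA-cell part rests on the assumption that the rows report the patient-level category.

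**What to change.** 1. Change the first apixaban renal row to serum creatinine <1.5 mg/dl *and* creatinine clearance ≥30 mL/min. Leave the second row and the 15-29 limit in 7.2.17 unchanged.
2. State in a footnote whether the rows of Table 51 report the patient-level category of 7.2.17. If they do, open the six apixaban NA cells: Underdosed in the age ≥80, weight ≤60 kg and second renal rows; Overdosed in the age <80, weight >60 kg and first renal rows. Every apixaban patient with known values then has exactly one cell in each pair.
3. On the same condition, check the dabigatran and edoxaban NA cells against 7.2.17.

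The cost is one word, a footnote and, if the condition applies, six apixaban cells plus any found for the other two drugs, with the matching program lines. No new data are needed.

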1. ABBREVIATIONS

ACE	Angiotensin Converting Enzyme inhibitors
ADR	Adverse Drug Reaction
AF	Atrial Fibrillation
AIDs	Acquired immune deficiency syndrome
ALT	Alanine Aminotransferase
ARB	Angiotensin-Receptor Blockers
AST	Aspartate Aminotransferase
BI	Boehringer Ingelheim
BID	Twice a day
BMI	Body Mass Index
CABG	Coronary Artery Bypass Grafting
CCI	Charlson Comorbidity Index
CFS	Clinical Frailty Scale
CHA2DS2-VASc	Congestive heart failure, Hypertension, Age (> 75), Diabetes mellitus, Stroke/TIA, Vascular disease, Age 65-74, Sex Category
CI	Confidence Interval
CKD	Chronic Kidney Disease
CRF	Case Report Form
eCRF	Electronic Case Report Form
EHRA	European Heart Rhythm Association
GFR	Glomerular Filtration Rate
HAS-BLED	Hypertension, Abnormal renal and liver function, Stroke (1 point), Bleeding history or predisposition, Labile INR, Elderly (>65 years), Drugs and Alcohol.
ICH	Intracranial haemorrhage
ICH-GCP	Harmonized Tripartite Guideline for Good Clinical Practice
INR	International Normalized Ratio
LVEF	Left ventricular ejection fraction
NSAIDs	Nonsteroidal Anti-Inflammatory Drugs
NYHA	New York Heart Association
NOAC	Non-vitamin K antagonist oral anticoagulant
NVAF	Non-valvular atrial fibrillation
OAC	Oral anticoagulant
PCI	Percutaneous coronary intervention

Document: H:\HOR-Europe\2019\2512352 - Study on anticoagulation management - BI\Proyecto\Estadistica\SAP\S AP_REBELD_version1.0_08072020.docx

Author: [REDACTED] Version Number: Version 1.0
Version Date: [08072020]

Template No.: RWI_TP_BIOS0013 Revision 1

Reference: RWI_WI_BIOS0015

Effective Date: 15Jun2018

PT	Preferred Terms
QD	Once a day
SADR	Serious Adverse Drug Reaction
SAHS	Sleep apnoea-hypopnoea syndrome
SAP	Statistical Analysis Plan
SmPC	Summary of Product Characteristics
SOC	System Organ Classes
SOPs	Standard Operating Procedures
TIA	Transitory ischemic attack
TLF	Tables/Listings/Figures
VKA	Vitamin K Antagonist

Document: H:\HOR-Europe\2019\2512352 - Study on anticoagulation management - BI\Proyecto\Estadistica\SAP\SAP_REBELD_version1.0_08072020.docx

Author: [Redacted]

Version Number: Version 1.0

Version Date: [08072020]

Template No.: RWI_TP_BIOS0013 Revision 1

Reference: RWI_WI_BIOS0015

Effective Date: 15Jun2018

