4.6 Changes to Analysis from Protocol

Per protocol, the variable “reason for VKA switch will be described under the OAC treatment management outcome. Finally, reason for VKA treatment switch has not been collected specifically in the VKA section of the CRF. This has been deleted from section 14.2.2 of SAP.

New analysis not included in the final protocol have been considered:

- Antiplatelet treatment according to current NOAC type
- Treatment received at the moment of thromboembolic and bleeding events.
- For all NOACs, the different doses that patients take according to HAS-BLED score.
- Underdosed and overdosed patients (for current NOAC treatment).
- HAS-BLED total score according to NOAC and antiplatelet current treatment.
- Multivariate model to evaluate the association between the Clinical Frailty Scale (dependent variable) and the thromboembolic and the bleeding events (independent variables). To calculate this analysis, only events that have occurred subsequent to the start of anticoagulant therapy (not those prior to the start of VKA / NOACs) will be considered. Univariate analysis will be performed. All variables which have a P value of less than 0.1 will be included in the multivariate analysis.

Document:	H:\HOR-Europe\2019\2512352 - Study on anticoagulation management - BI\Proyecto\Estadistica\SAP\S		
	AP_REBELD_version1.0_08072020.docx		
Author:	██████████	Version Number:	Version 1.0
		Version Date:	[08072020]

Template No.: RWI_TP_BIOS0013 Revision 1

Reference: RWI_WI_BIOS0015

Effective Date: 15Jun2018

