6.2 Full Analysis Set [FAS]

The full analysis set (FAS) will contain all enrolled subjects who provide informed consent for this study (ENR set) and fulfill all selection criteria. This is called “eligible patients” in the protocol.

Patients will be included in FAS if all of the following criteria are met:

1. Patients are willing and provide written informed consent prior to participate in this study
2. Patients \geq 75 years-old at the time of the study visit.
3. Patients with a diagnosis of non-valvular atrial fibrillation (NVAf).

Document:	H:\HOR-Europe\2019\2512352 - Study on anticoagulation management - BI\Proyecto\Estadistica\SAP\SAP_REBELD_version1.0_08072020.docx		
Author:	[REDACTED]	Version Number:	Version 1.0
		Version Date:	[08072020]

Template No.: RWI_TP_BIOS0013 Revision 1

Reference: RWI_WI_BIOS0015

Effective Date: 15Jun2018

4. Patients who are being treated with NOAC treatment according to the indication approved in the SmPC.
5. Patients who have started the NOAC treatment at least 3 months prior to the study visit.

Patients will be excluded from participating in this study, and will be excluded from this analysis set, if the following criterion is met:

1. Current participation in any clinical trial of a drug or device.
2. Patients who have any contraindication for NOAC treatment, according to the SmPC.

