8.5 Examination of Subgroups

Subgroup analyses will be conducted as stated in the exploratory analysis sections. It should be noted that the study was not designed to detect treatment differences within subgroups. The following subgroups will be assessed and described within the exploratory analysis sections (a minimum of 50 patients will be required for each subgroups).

For the primary objective (the pattern of NOAC usage):

- Sex:
 - Female
 - Male
- Age at the time of the study visit:
 - 75-79 years
 - 80-84 years
 - ≥ 85 years
- Presence of each comorbidities at the time of the study visit (heart failure, coronary artery disease, peripheral vascular disease diabetes, chronic kidney disease, liver disease, cancer):
 - No
 - Yes

For the secondary objectives (Patient's characteristics at the time of the study visit and OAC treatment management):

- Duration since the first NOAC initiation date until the study visit:

Document:	H:\HOR-Europe\2019\2512352 - Study on anticoagulation management - BI\Proyecto\Estadistica\SAP\S		
	AP_REBELD_version1.0_08072020.docx		
Author:	██████████	Version Number:	Version 1.0
		Version Date:	[08072020]

Template No.: RWI_TP_BIOS0013 Revision 1

Reference: RWI_WI_BIOS0015

Effective Date: 15Jun2018

- ≤4 months
- > 4 months

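### Table 52 splits HAS-BLED by single NOAC-antiplatelet pairs without specifying a NOAC-alone or pooled row, so most of its row percentages would say little

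*SAP*

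**What the plan says.** SAP 4.6 lists "HAS-BLED total score according to NOAC and antiplatelet current treatment" among the analyses added after the protocol. SAP 14.6 (exploratory analysis) says that the total score, grouped as <3, 3-5 and ≥5, "will be described according to NOAC and antiplatelet current treatment".

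The shell is Table 52 in SAP 17.4, titled "HAS-BLED score according NOAC+antiplatelet current treatment". Its first row is "Dabigatran+aspirin". The next two rows pair dabigatran with one other named agent each, and the remainder is an ellipsis with a note that all combinations are to be shown. Percentages are by row, and each row carries a valid N. No row for a NOAC without an antiplatelet, for any antiplatelet, or for a total is written out.

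Other parts of the SAP bear on this:

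- Tables 41 and 45 give current antiplatelet treatment as 'None' plus nine levels (eight named agents and 'Others').
- Table 15 gives HAS-BLED by current NOAC for all patients, without separating antiplatelet users from non-users.
- The abbreviation list expands the end of the HAS-BLED acronym as "Bleeding history or predisposition, Labile INR, Elderly (>65 years), Drugs and Alcohol". It does not say which drugs score.
- SAP Table 3 lists only the HAS-BLED total as collected.
- SAP 7.2.16 sets high bleeding risk at a score of 3 or more.

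**The concern.** A table of HAS-BLED by combined treatment will naturally be read for how bleeding risk differs between patients with and without an antiplatelet on top of the NOAC. The layout gets in the way of that reading in three respects.

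First, the group against which co-treated patients would be compared is not specified. Second, splitting by single agent spreads a limited number of co-treated patients over many rows, each with its own denominator. Third, the score that fills the columns may itself contain a point for the treatment that defines the rows, and the SAP neither notes this nor plans a score without that item.

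What is at stake is the interpretation of one exploratory table.

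**Working it through.** The documents state no figure for this table, so there is none to reproduce. Three checks follow.

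**1. Number and size of rows.** Inputs: 4 NOACs (Table 52 and the other shells); 9 antiplatelet levels excluding 'None' (Tables 41 and 45); about 500 patients (SAP 4.2). The share on an antiplatelet is not in the documents, so it is assumed at 10-30%.

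Single-agent rows = 4 × 9 = 36, before any dual antiplatelet therapy. Adding 'None' for each NOAC gives 4 × 10 = 40.

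| Assumed antiplatelet use | Co-treated patients | Mean per row (÷ 36) |
|---|---|---|
| 10% | 50 | 1.4 |
| 20% | 100 | 2.8 |
| 30% | 150 | 4.2 |

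These are averages, and use will concentrate in the common agents. As a favourable case, suppose all 100 patients of the 20% scenario took one of just two agents, spread evenly over the four NOACs: 100 / 8 = 12.5 per row, with the other 28 rows empty. Exact (Clopper-Pearson) 95% intervals show what such rows can carry: 1 of 3 gives 0.8% to 90.6%; 4 of 12 gives 9.9% to 65.1%.

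**2. Possible overlap between score and row.** Every patient in the full analysis set is at least "75 years-old at the time of the study visit", so everyone scores the elderly item. If antiplatelets count under drugs, a co-treated patient with no other item scores 1 + 1 = 2. That falls in the <3 column and in the SAP's intermediate class. Co-treatment alone therefore does not place a patient at ≥3; it lowers the number of further points needed from 2 to 1.

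To gauge the size, assume score distributions without the drugs point (1 / 2 / 3 / 4+) and shift them by one:

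| Assumed distribution, % | Share ≥3 without the point | Share ≥3 with it |
|---|---|---|
| 50 / 35 / 12 / 3 | 12 + 3 = 15% | 35 + 12 + 3 = 50% |
| 35 / 40 / 18 / 7 | 18 + 7 = 25% | 40 + 18 + 7 = 65% |
| 25 / 40 / 25 / 10 | 25 + 10 = 35% | 40 + 25 + 10 = 75% |

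A second model takes k other independent one-point items, each present with probability q. Then P(≥3) is P(Bin(k, q) ≥ 2) without the point and P(Bin(k, q) ≥ 1) with it: 11% against 47% (k = 6, q = 0.1), 35% against 74% (k = 6, q = 0.2), and 67% against 92% (k = 7, q = 0.3).

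So the shift ranges from zero, if antiplatelets do not score, to roughly 25-40 percentage points under these assumptions if they do.

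**3. Column limits.** The columns are <3, 3-5 and ≥5. A score of 5 satisfies both of the last two, so row percentages could sum to more than 100%.

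**The case against.** Table 52 is a mock shell with three example rows. 'All combinations', read with the 'None' level of Tables 41 and 45, could include NOAC alone, and SAP 14.6 does not restrict the description to co-treated patients. That stands: the reference row is unspecified rather than excluded. The same wording could equally include dual therapy, so the shell leaves the programmer to decide both. Table 15 offers a comparator by NOAC, but a mixed one.

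A reader might infer that co-treated patients become high-risk by construction. The documents do not support this: elderly plus drugs makes 2, still below 3, and nothing says that antiplatelets score at all.

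A reader might also infer that the SAP breaks its own rule that "a minimum of 50 patients will be required for each subgroups". SAP 8.5 attaches that minimum to sex, age, comorbidity and time since first NOAC. NOAC-antiplatelet combinations are not listed, so the rule does not formally apply; it is at most a yardstick.

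It is also fair that describing the total score in patients on combined treatment is legitimate without removing an item, that the SAP never says the table should show risk net of co-treatment, and that the printed valid N makes small denominators visible. These points lower the weight of the overlap. They do not make a table of mostly tiny rows more useful.

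**Conclusion.** The point holds as a layout weakness. The single-agent split gives 36 rows averaging 1.4-4.2 patients at an assumed 10-30% antiplatelet use, and no NOAC-alone or pooled row is specified. The row count follows from the SAP; the averages rest on the assumed use and describe an uneven spread. The conclusion about sparse rows does not depend on how HAS-BLED was scored.

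The overlap with the drugs item is conditional: one point upward for co-treated patients if antiplatelets count, nothing if they do not. The percentage-point illustrations rest on assumed score distributions and should not be quoted as expected effects. The shared score of 5 is a plain error in the same table.

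The analysis is exploratory and descriptive, with no test attached to it and no effect on any primary or secondary result. Severity is minor.

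**What to change.** In SAP 14.6 and Table 52:

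1. Specify the rows 'NOAC alone', 'NOAC + one antiplatelet' and 'NOAC + two or more antiplatelets', within each NOAC and overall, and give percentages on these rows. That is 4 × 3 + 3 = 15 rows. At the same assumed use, co-treated patients would number 50-150 overall and average 12.5-37.5 per NOAC (50 / 4 to 150 / 4).
2. List single-agent combinations as counts where rows are small.
3. Add a footnote that HAS-BLED has a drugs item that may overlap with the row definition. Show a score without that point only if the sponsor confirms how the item was defined and scored, because only an investigator-entered total is listed as collected.
4. Make the upper two score columns mutually exclusive.

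The cost is one revised shell and a sentence of SAP text, using data already collected. The downside is that percentages for single agents are lost where rows are small.
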